13.6.3 Secondary Endpoint(s)

All Patients:

- Change in quality of life as measured with QOLCE if 18 years of age or younger, or QOLIE if 19 years of age or older, relative to the pre-randomization baseline of the Core Study, if assessed during the Core Study.
- Change in S/CGIC, relative to the pre-randomization baseline of the Core Study.
- Change in adaptive behavior as measured with the Vineland-II, relative to the pre-randomization baseline of the Core Study, if assessed during the Core Study.
- Change in the number of inpatient epilepsy-related hospitalizations (number of hospitalizations due to epilepsy in each 28-day period), relative to the pre-randomization baseline of the Core Study.
- Change in the use of rescue medication (number of days used in each 28-day period), relative to the pre-randomization baseline of the Core Study.
- Maintenance of seizure frequency reduction and freedom from seizures during the OLE study.
- Percentage change in the frequency of total seizures, relative to the pre-randomization baseline of the Core Study.
- Number of patients considered treatment responders, defined as those with a $\geq 25\%$, $\geq 50\%$, $\geq 75\%$, or 100% reduction in total seizures, relative to the pre-randomization baseline of the Core Study.
- Number of patients experiencing a $> 25\%$ worsening, -25 to $+25\%$ no change, $25-50\%$ improvement, $50-75\%$ improvement or $> 75\%$ improvement in total seizures, relative to the pre-randomization baseline of the Core Study.
- Percentage change in the frequencies of subtypes of seizures, relative to the pre-randomization baseline of the Core Study.

- Changes in duration of seizure subtypes as assessed by the S/CGICSD, relative to the pre-randomization baseline of the Core Study.
- Change in the number of episodes of *status epilepticus*, relative to the pre-randomization baseline of the Core Study.
- Change in cognitive function as measured with a cognitive assessment battery, relative to the pre-randomization baseline of the Core Study, if assessed during the Core Study.
- Change in growth and development for patients less than 18 years of age by measurement of height, weight, IGF-1 levels and Tanner Staging (for patients aged 10–17 [inclusive], or earlier if clinically indicated by onset of menarche or other signs of precocious puberty), relative to the pre-randomization baseline of the Core Study.
- Effects on menstruation cycles (in females).
- Drug abuse liability, as measured by AEs of abuse potential, drug accountability and Study Medication Use and Behavior Survey in patients aged 12 and older.

DS Patients Only:

- Percentage change in total convulsive seizure frequency, relative to the pre-randomization baseline of the Core Study.
- Percentage change in total non-convulsive seizure frequency, relative to the pre-randomization baseline of the Core Study.
- Number of patients considered treatment responders, defined as those with a $\geq 25\%$, $\geq 50\%$, $\geq 75\%$, or 100% reduction in convulsive seizures, relative to the pre-randomization baseline of the Core Study.
- Number of patients experiencing a $> 25\%$ worsening, $- 25$ to $+ 25\%$ no change, 25 – 50% improvement, 50 – 75% improvement or $> 75\%$ improvement in convulsive seizures, relative to the pre-randomization baseline of the Core Study.

LGS Patients Only:

- Percentage change in the number of drop seizures, relative to the pre-randomization baseline of the Core Study.
- Percentage change in the number of non-drop seizures, relative to the pre-randomization baseline of the Core Study.
- Number of patients considered treatment responders, defined as those with a $\geq 25\%$, $\geq 50\%$, $\geq 75\%$, or 100% reduction in drop seizures, relative to the pre-randomization baseline of the Core Study.
- Number of patients experiencing a $> 25\%$ worsening, $- 25$ to $+ 25\%$ no change, 25 – 50% improvement, 50 – 75% improvement or $> 75\%$ improvement in drop seizures, relative to the pre-randomization baseline of the Core Study.

These will be summarized across time, using appropriate statistical methods.
Descriptive statistical methods will be used throughout. There will be no formal hypothesis testing.

14 DATA SAFETY MONITORING COMMITTEE

This study will not use a DSMC.

15 REGULATORY AND ETHICAL OBLIGATIONS

15.1 Declaration of Helsinki

The Investigator will ensure that this study is conducted in full conformity with the Declaration of Helsinki⁷³, EU Clinical Trials Directive⁷⁷ and the clinical trial regulations adopting European Commission Directives into national legislation^{79,80,81}.

15.2 Informed Consent/Assent

Initial master informed consent and assent forms will be provided to the Investigator to prepare the informed consent/assent documents to be used at his or her center. The GW Clinical Manager will communicate updates to the template by letter. The written informed consent/assent documents should be prepared in the language(s) of the potential patient population.

Before a patient's participation in the trial, the Investigator is responsible for obtaining written informed consent/assent from the patient and/or parent(s)/legal representative after adequate explanation of the aims, methods, anticipated benefits and potential hazards of the study and before any protocol specific screening procedures or any IMPs are administered. The patient and parent(s)/legal representative should have ample time for review to consider the information provided before giving written consent/assent; more specific definitions of ample time may be in force if required by ECs/IRBs or local regulations.

The acquisition of informed consent/assent should be documented in the patient's medical records and the informed consent/assent forms should be signed and personally dated by the patient and/or parent(s)/legal representative (as applicable) and by the person who conducted the informed consent/assent discussion. GW also requires a physician to be present for consent/assent and to sign the consent/assent forms as well. The original signed informed consent/assent forms should be retained and a copy provided to the patient and/or parent(s)/legal representative.

15.3 Institutional Review Board/Ethics Committee

A copy of the protocol, proposed informed consent/assent forms, other patient information material, any proposed advertising material and any further documentation requested must be submitted to the IRB/EC for written approval. GW must receive a copy of the written approval of the protocol and informed consent/assent forms before enrollment of patients into the study and shipment of IMP.

The Investigator must submit and, where necessary, obtain approval from the IRB/EC for all subsequent protocol amendments and changes to the informed consent/assent documents. The Investigator should notify the IRB/EC of deviations from the protocol or SAEs occurring at the center and other AE reports received from GW, in accordance with local procedures.

The Investigator will be responsible for obtaining on-going IRB/EC approval/renewal throughout the duration of the study. Copies of the Investigator's reports and the IRB/EC continuance of approval must be sent to GW.

15.4 Pre-Study Documentation Requirements

The Investigator is responsible for forwarding the following documents to GW for review before allowing any patients to consent/assent for entry into the study:

- Signed and dated protocol signature page.
- Copy of approved informed consent/assent forms and other patient information material.
- Copy of the IRB/EC approval of the protocol, informed consent/assent forms and other patient information material.
- Up to date curriculum vitae and medical licenses (as per local regulations) of the PI and all sub-Investigators.
- The IRB/EC composition and/or written statement of the IRB/EC in compliance with the FDA regulations relating to GCP and clinical trials^{74,75,76,82}, the EU Clinical Trials Directive⁷⁷, or International Conference on Harmonization Tripartite Guideline for Good Clinical Practice (ICH GCP)⁸³ where the EU Clinical Trials Directive does not apply.
- Signed laboratory normal ranges and documentation of laboratory certification (or equivalent) unless using central laboratory arranged by GW.
- Signed clinical trial agreement (including patient/Investigator indemnity insurance and financial agreement).
- FDA 1572 form.
- Completed financial disclosure statements for the PI and all sub-Investigators if relevant.

15.5 Patient Confidentiality

The Investigator must ensure that the patient's anonymity is maintained. On the CRFs and within the databases used to collect the trial data or other documents submitted to GW, patients should be identified by their initials and race (if allowed per local regulations) and a patient study number only. Documents that are not for submission to GW, e.g., signed informed consent/assent forms, should be kept in strict confidence by the Investigator.

In compliance with the FDA regulations relating to GCP and clinical trials^{74,75,76,82}, and the EU Clinical Trials Directive⁷⁷/ICH GCP Guidelines⁸³, it is required that the Investigator and institution permit authorized representatives of the company, the regulatory agencies and the IRB/EC direct access to review the patient's original medical records for verification of study-related procedures and data. Direct access includes examining, analyzing, verifying and reproducing any records and reports that are important to the evaluation of the study. The Investigator is obligated to inform the patient that his/her study-related records will be reviewed by the above named representatives without violating the confidentiality of the patient.

All information concerning the IMP and operations of GW such as patent applications, formulae, manufacturing processes, basic scientific data or formulation information supplied to the Investigator by the company and not previously published is considered confidential by the company and shall remain the sole property of the company. The Investigator will agree to use this information only in accomplishing the study and will not use it for any other purposes without the written consent of the company.

16 ADMINISTRATIVE AND LEGAL OBLIGATIONS

16.1 Protocol Amendments and End of Study or Termination

Protocol amendments must be made only with the prior approval of GW. Agreement from the Investigator must be obtained for all protocol amendments and amendments to the informed consent/assent documents. The IRB/EC must be informed of all amendments and give approval for any substantial amendments. Amendments for administrative changes can be submitted to the IRB/EC for information only. The Investigator must send a copy of the approval letter from the IRB/EC to GW.

Both GW and the Investigator reserve the right to terminate the study, according to the clinical trial agreement. The Investigator should notify the IRB/EC in writing of the study's completion or early termination and send a copy of the notification to GW.

16.2 Study Documentation and Storage

The Investigator should maintain a list of appropriately qualified persons to whom he/she has delegated study duties. All persons authorized to make entries and/or corrections on CRFs will be included on the GW delegation of authority and signature form.

Source documents are original documents, data and records from which the patient's CRF data are obtained. These include, but are not limited to, hospital records, clinical and office charts, laboratory and pharmacy records, diaries, electronic data captured by IVRS, microfiches, radiographs and correspondence. CRF entries may be considered source data if the CRF is the site of the original recording, that is, there is no other written or electronic record of data. A source data verification plan, identifying the source for each data point at each site, will be agreed with each site prior to patient recruitment. In the rare situations of data being recorded directly into the CRF in error, then the source data from the CRF should be transcribed into the patient's notes with appropriate signature and date to provide a full audit trail.

The Investigator and study staff are responsible for maintaining a comprehensive and centralized filing system of all study-related, essential documentation (as outlined in ICH E6 Section 8.2⁸³), suitable for inspection at any time by representatives from GW and/or applicable regulatory authorities. Elements should include:

- Patient files containing completed CRFs, informed consent/assent forms and supporting copies of source documentation.
- Study files containing the protocol with all amendments, IB, copies of pre-study documentation (see [Section 15.4](#)) and all correspondence to and from the IRB/EC and GW.

- Proof of receipt, IMP accountability record, return of IMP for destruction, final IMP reconciliation statement and all drug related correspondence.

In addition, all original source documents supporting entries on the CRFs, diary data and electronic data captured by IVRS must be maintained and be readily available.

Following completion or termination of a clinical study GW will initiate proper archive of clinical study-related documentation and electronic records generated by the Investigator and/or GW. All clinical trial related documents and electronic records will be retained within an archiving system for a period dependent upon need and for a minimum of 20 years. Essential documents should be retained until at least 2 years after the last approval of a marketing application in an ICH region and until there are no pending or contemplated marketing applications in an ICH region or at least 2 years have elapsed since the formal discontinuation of clinical development of the IMP. These documents should be retained for a longer period however if required by the applicable regulatory requirements or if needed by GW (EU Directive 2005/28/EC Chapter 4 Trial Master File and Archiving Article 16⁸⁴).

GW will inform the Investigators for each center in writing of the need for record retention. No study document should be destroyed without prior written agreement between GW and the Investigator. Should the Investigator wish to assign the study records to another party or move them to another location, he/she must notify GW in writing of the new responsible person and/or the new location.

16.3 Study Monitoring and Data Collection

The GW representative and regulatory authority inspectors are responsible for contacting and visiting the Investigator for the purpose of inspecting the facilities and, upon request, inspecting the various records of the study for example, CRFs and other pertinent data provided that patient confidentiality is respected.

The GW study monitor, or designee, is responsible for inspecting the CRFs and available IVRS/diary data at regular intervals throughout the study to verify adherence to the protocol, completeness, accuracy and consistency of the data and adherence to local regulations on the conduct of clinical research. The study monitor should have access to patient medical records and other study-related records needed to verify the entries on the CRFs.

The Investigator agrees to co-operate with the study monitor to ensure that any problems detected in the course of these monitoring visits are resolved.

The Investigator is responsible for ensuring the data recorded in the CRFs are accurate and complete. The CRF should be completed within 5 working days after

the patient's visit and before review by the study monitor. Queries generated by GW or its representative are to be answered within a similar period of time. Shorter periods of time may apply during specific situations such as interim analysis or final database cleaning.

All handwritten medical records should be filled out with a black or blue ball-point pen and must be legible. Corrections to paper forms will be made by a single line stroke through the error and insertion of the correction above or beside the error. The change must be initialed and dated by the Investigator or a member of the study staff authorized by the Investigator. No correction fluid or tape may be used. The PI will sign and date the indicated places on the CRF. These signatures will indicate that the PI inspected or reviewed the data on the CRF, the data queries and the site notifications and agrees with the content.

To ensure the quality of clinical data across all patients and centers, a clinical data management review will be performed on patient data received at GW or a contract research organization (CRO). During this review, patient data will be checked for consistency, omissions and any apparent discrepancies. In addition, the data will be reviewed for adherence to the protocol and FDA regulations^{74,75,76,82}, the ICH GCP Guideline⁸³, and all other applicable regulatory requirements; to resolve any questions arising from the clinical data management review process, data queries and/or center notifications will be sent to the center for completion and then returned to GW or the CRO, as applicable.

GW's or the CRO's Clinical Data Management Department will correct the following issues in CRFs without any notification to site staff:

- Misspellings that do not change the meaning of the word, excluding AEs and medications.
- Date errors that occur at the end of the year and into the New Year.
- Temperature unit errors (Fahrenheit vs Centigrade).
- Weight unit errors (pounds vs kilograms) if a baseline weight has been established.
- Administrative data, for example, event names for unscheduled visits or retests.
- Clarifying "other, specify" if data are provided for example, race, physical exam.
- If a YES or NO question for example, 'Were there any AEs?' is left blank yet AEs are listed on the CRF, YES will be entered in the blank.
- Correct CRF page numbers.

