Baseline	The 28-day period of the Core Study from screening to randomization.
Convulsive seizures	Tonic-clonic, tonic, clonic or atonic seizures.
Core Study	A double-blind, randomized, placebo-controlled, parallel group study of GWP42003-P in patients with DS or LGS.
Countable partial seizures	Partial/focal seizures with a motor or behavioral component that allow such seizures to be easily identified and hence counted.
Day 1	The day a patient first receives investigational medicinal product in this study.
Drop seizure	An attack or spell (atonic, tonic or tonic-clonic) involving the entire body, trunk or head that led or may have led to a fall, injury, slumping in a chair or hitting the patient's head on a surface.
Enrolled patient	Patient is considered enrolled in the study from the time of providing written informed consent/assent.
End of treatment	A maximum of 4 years' (208 weeks after Visit 1) treatment.
End of study	Last patient last visit or last contact, whichever occurs last.
IMP	Investigational Medicinal Product (Study Medication).
INR	International Normalized Ratio (INR) is a calculation made to standardize prothrombin time.
Investigator	Study Principal Investigator or a formally delegated study physician.
Non-convulsive seizures	Myoclonic, partial or absence seizures.
Non-drop seizures	Seizures that would not result in a fall or drop attack.
Status epilepticus	Any seizure lasting for 30 minutes or longer.
Subtypes of seizures	Protocol seizure subtypes can be atonic, tonic, clonic, tonic-clonic, myoclonic, absence, countable partial and other partial.

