8.1.2 Dose Escalation, Dose Adjustments and Down-Titration

The titration regimen is shown in [APPENDIX 4](#). All patients will titrate up to a target dose of 10–20 mg/kg/day GWP42003-P.

Patients will be weighed at each study visit. During Visit 1, the daily volumes of IMP solution to be taken during the titration period will be calculated via the IVRS and the dosing regimen provided to the patient and/or caregiver. Patients should aim to achieve the target dose before the end of the 2-week titration period; however, Investigators may decrease the dose if a patient experiences intolerance, or increase the dose if required for better seizure control, until the optimal dose is found. The titration period will be considered 2 weeks long to ensure most patients have achieved stable dosing from Visit 2 onwards (maintenance period). The rate of titration should be adjusted based on the specific needs of an individual patient. It is advised that the Investigator considers monitoring hepatic function (ALT, AST, TBL and INR levels) during the titration period for patients taking AEDs that are known to be associated with hepatic injury or failure. To minimize any elevations in hepatic function markers the titration period can be extended and the dosage of a concomitant AED and/or GWP42003-P may be adjusted at the discretion of the Investigator. If there is intolerance during titration, the patient may be maintained on a dose below 10-20 mg/kg/day. A titration rate faster than recommended may be considered if there is an increase in seizures, following consultation with the GW medical monitor. Further information on dispensing procedures will be provided in a separate Pharmacy Manual.

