4.5.8.13 Exposure to Study Medication

Patients are required to take IMP twice daily (morning and evening). The first OLE dose will be taken in the clinic on Visit 1 (Day 1). The date of final dose in the study will be recorded on the CRF. The date of final dose, for patients who enter the taper period, will be recorded on the CRF at the end of taper visit.

The total number of dosing days in the study will be calculated as:

$$(\text{Date of last dose in the treatment phase} - \text{Date of Day 1}) + 1$$

The date of last dose in the treatment phase will be obtained from the CRF at the end of treatment visit.

The total number of dosing days in the study will be summarized for all patients, and patients who completed the treatment phase. The modal dose will be calculated for each patient over the same periods associated with IVRS calls for seizure reporting and will subsequently be summarized. Furthermore, a categorical summary of patients whose largest dose was 20 mg/kg/day or less, patients whose largest dose was over 20 mg/kg/day and less than 30 mg/kg/day, and patients whose largest dose was 30 mg/kg/day or more during the OLE study will be presented.

The above summaries will be repeated for the following subgroups:

- Excluding data for patients from study GWEP1332 Part A
- Patients taking clobazam
- Patients not taking clobazam
- Core study actual treatment: GWP42003-P
- Core study actual treatment: Placebo
- Patients taking clobazam; core study actual treatment: GWP42003-P
- Patients not taking clobazam; core study actual treatment: GWP42003-P
- Patients taking clobazam; core study actual treatment: Placebo
- Patients not taking clobazam; core study actual treatment: Placebo

The modal dose for each patient will be calculated across their entire period of exposure, and the number of patients and patient-years exposure will be summarized in the following groups:

- $\leq 20\text{mg/kg/day}$
- $20 - < 25\text{mg/kg/day}$
- $\geq 25\text{mg/kg/day}$

For each group, the total number of patient-years of exposure will be calculated as the sum of the total number of dosing days for each patient divided by 365.25. For the calculation of modal dose, patients will be assumed to be taking 20 mg/kg/day unless a dose adjustment is recorded.

Any missed doses during treatment should be recorded on the 'IMP Missed Doses Log' CRF page.

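### Pound/kilogram weight errors in the CRF are corrected without telling the site, and nothing requires a check of whether the same wrong unit was used in the IVRS to set the dose

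*Protocol*

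**What the plan says.** Protocol 16.3 (Study Monitoring and Data Collection) sets a default route for discrepancies: "data queries and/or center notifications will be sent to the center for completion and then returned to GW or the CRO, as applicable". It then exempts a short list. For those items the "Clinical Data Management Department will correct the following issues in CRFs without any notification to site staff". The list includes "Weight unit errors (pounds vs kilograms) if a baseline weight has been established".

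The proviso about a baseline weight exempts little. The Definition of Terms gives baseline as "The 28-day period of the Core Study from screening to randomization", so a patient entering the extension would normally already meet the condition at Visit 1.

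Elsewhere the protocol makes weight a determinant of dose:
- 8.1.2: patients are weighed at every study visit, and "During Visit 1, the daily volumes of IMP solution to be taken during the titration period will be calculated via the IVRS". The IVRS also generates the taper volumes.
- 5.2.1: the quantity dispensed at each visit depends on the chosen dose and the patient's weight.
- Appendix 4: every titration step is expressed in mg/kg.
- 8.1.2: the stated maximum is 30 mg/kg/day.

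**The concern.** For most fields on the silent list, correcting an obvious slip without a query is sensible. Weight differs because the number recorded at the visit may also be the number that set the volume the patient takes. A CRF weight in the wrong unit is a reason to ask which weight the IVRS holds. Under 16.3 the CRF value is put right and nobody has to ask.

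The rule also sits awkwardly with the rest of 16.3. Silent spelling corrections exclude adverse events and medications, so safety-relevant fields were evidently meant to be protected. The principal investigator's signature attests to review of the CRF data, the queries and the site notifications, and a silent correction generates neither a query nor a notification.

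What is at stake is a possible dosing-weight error going unexamined in a study whose primary objective is safety under weight-based dosing.

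**Working it through.** The documents state no figure on this point, so there is nothing to reproduce. The check is unit arithmetic plus a comparison of provisions.

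**Inputs**
- Conversion: 1 kg = 2.2046 lb (standard constant, not in the documents).
- Concentration: 100 mg/mL (Protocol 5.1, 8.1).
- Example dose: 20 mg/kg/day (Appendix 4, Days 11–14).
- Stated maximum: 30 mg/kg/day (8.1.2).
- Assumed patient weight for the volume example: 20 kg, with a range of 10 to 70 kg.
- Assumption for every dose figure: the wrong unit was also used in the IVRS.

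**Delivered dose**
- Pounds taken as kilograms: delivered = intended × 2.2046. So 20 × 2.2046 = 44.1 mg/kg/day, and 44.1 / 30 = 1.47, which is 47% above the stated maximum. An intended 10 becomes 22.0, and an intended 30 becomes 66.1.
- Smallest intended dose that would pass the stated maximum: 30 / 2.2046 = 13.6 mg/kg/day.
- Kilograms taken as pounds: delivered = intended / 2.2046 = intended × 0.454. So 20 becomes 9.1 mg/kg/day.

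**Volume** = weight (kg) × dose (mg/kg/day) / 100
- 20 kg patient: 20 × 20 / 100 = 4.0 mL/day intended. With 44.09 used as kilograms, 44.09 × 20 / 100 = 8.8 mL/day.
- 10 kg: 2.0 becomes 4.4 mL/day. 70 kg: 14.0 becomes 30.9 mL/day.

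**How visible the CRF error is before correction**
- Pounds as kilograms: (2.2046 − 1) × 100 = +120% apparent weight change.
- Reverse: (0.4536 − 1) × 100 = −55%.
- SAP Appendix 2, Table 7 flags a weight change of 7% or more in either direction. An uncorrected unit error would stand far outside that limit; once corrected, the signal is gone.

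**What links the CRF correction to the IVRS**
- 16.3 applies to CRFs only.
- 8.1.2 calculates titration volumes at Visit 1, whereas 16.3 allows up to 5 working days after a visit to complete the CRF. The two entries can therefore be separate.
- Neither document says that the CRF weight feeds the IVRS, or that both come from one entry. Neither excludes it.
- Neither document requires the IVRS weight to be compared when a CRF weight is corrected.

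**The case against.** The strongest reply is that the harmful chain is not in the documents. The CRF may be a later transcription, and a unit slip made there changes nothing the patient took. Dispensing details sit in a separate Pharmacy Manual, so unit or range checks in the IVRS cannot be judged from here. This stands, and it makes the point conditional.

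Several stronger readings are tempting but unsupported:
- **A reader might infer that the error is erased from the data.** Only the CRF value changes. Source documents are retained (16.2), and IVRS data are held separately with an audit trail (16.4).
- **That nobody will ask.** The monitor inspects CRFs and available IVRS data with access to medical records (16.3), patients are re-weighed at each visit, and returned product is checked. The rule disables none of these. They are chances to find the error, although none is tied to the correction.
- **That a wrong dose would run for the 24 to 28 weeks between later visits.** The documents describe IVRS volume calculation for titration and taper. They do not describe recalculating maintenance volumes from each visit's weight. For an error at Visit 1, the next scheduled weighing is two weeks later.
- **That it would create a false abuse trigger.** The triggers in 9.1.15.2.1 compare use with expected use or target dose. If those rest on the same wrong weight, the trigger could equally be suppressed.
- **That the SAP's exposure rule is part of the same fault.** SAP 4.5.8.13 says that for modal dose "patients will be assumed to be taking 20 mg/kg/day unless a dose adjustment is recorded". That applies to every patient whatever 16.3 says, and is a separate matter.

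**Conclusion.** The concern holds in a narrow, conditional form. Protocol 16.3 exempts pound/kilogram errors from site notification although weight determines dosing volumes, and no IVRS check is required in its place. If the IVRS used the same wrong unit, the dose would be wrong by a factor of 2.2 or 0.45, and any intended dose above 13.6 mg/kg/day would exceed the protocol's own stated maximum when pounds are taken as kilograms. If the error was confined to the CRF, there is no dosing consequence and the correction is harmless.

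The documents do not settle which case applies, and they give no count of such errors, so no expected number of affected patients can be stated. What justifies a change is a cheap check set against a large possible error in an individual patient. This is a data-management improvement. It passes no judgment on any dose or clinical rule.

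**What to change.** Remove weight-unit errors from the silent-correction list in Protocol 16.3. For each such error:
1. Send a query to the site.
2. Check the weight held in the IVRS for that visit and the volumes issued since.
3. If the IVRS weight was wrong, record a protocol deviation.
4. For that interval, use the dose actually issued (mg issued divided by the corrected weight) in the exposure summaries of SAP 4.5.8.13, in place of the assumed or nominal dose.

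The other items on the silent list need not change. The cost is a few extra queries, one IVRS cross-check per error, and wording in the protocol or data management plan, with one sentence in the SAP.
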